- c. Patients with known or suspected atrioventricular nodal blockade process requiring cardiology evaluation and/or pacemaker placement
- d. Hemodynamic instability (defined as a new intravenous vasopressor or inotrope requirement [e.g., norepinephrine; epinephrine; phenylephrine; dobutamine; milrinone] or a mean arterial pressure < 55 mmHg)
- e. Signs of active myocardial ischemia or non-ST elevation MI
- f. Patients with greater than 20 rib fractures (20-mL vial [266-mg dose]; 1-mL [13.3 mg] per rib)
- g. Weight < 50 kg or > 150 kg
- h. Pregnancy as defined by urine pregnancy test in all females of child-bearing potential
- i. Incarceration
- j. Inability to obtain informed consent
- k. Severe traumatic brain injury, GCS <8

Patients will be followed for outcome assessment during hospitalization through discharge.

14. Consenting process and plan

Patients will be identified as previously described and permission to consent per the trauma team attending will be obtained prior to administration of consent. Study personnel will administer consent in the patient's room. Patients who meet inclusion and exclusion criteria will be eligible for consent. Informed consent will be obtained prior to randomization into treatment arms. Patients unable to give consent will have LAR or next of kin consented. LAR must show proof of health care POA or court document. A copy of the documents will be kept with the

consent form. Next of kin is a person who may act as LAR without a document granted by court. Next of kin will be determined by team social workers' note. The order in which the next of kin may act as LAR is: spouse, parent, adult son or daughter, adult brother or sister. If next of kin available at the time of consent cannot agree, the person cannot participate in the research. Investigators will be available seven days a week and will continue correspondence with subjects throughout the study for up to 7 days or until hospital discharge, whichever comes first.

Subjects can withdraw from the study at any time per their desire or may be withdrawn at the discretion of the trauma team. Subjects will be withdrawn as appropriate based on any adverse event that may occur as described above in Section 9. Any subject who withdraws will be placed on standard of care.

15. Compensation:

Patients will not receive any compensation for research involvement.

16. Subject costs:

There are no additional costs to subjects.

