emergency medicine and surgery practitioners are familiar with intercostal blocks for placement of tube thoracostomy. Intercostal blocks do not require additional training, as would be done in the setting of a pain medicine fellowship, and do not incur the risks of hypotension associated with epidural catheters. Additionally, intercostal and paravertebral blocks carry similar risks of pneumothorax or intercostal neurovascular bundle injury.

Study design:

This is an investigator-initiated, single-center, prospective, double-blinded, placebo-controlled trial funded by the United States Air Force. Multi-system, adult trauma patients greater than or equal to 18 years of age admitted to the University of Cincinnati Medical Center (UCMC), an urban American College of Surgeons-verified Level 1 trauma center with more than 3500 annual trauma admissions annually will be identified by the research team. Patients will be screened and those who meet all inclusion/exclusion criteria will be approached for informed consent by study personnel in their rooms. Informed consent will be obtained prior to enrollment and any study procedures are done. Patients will then receive either receive 1 mL of liposomal bupivacaine just below each affected rib or 0.9% sodium chloride peri-intercostal subcutaneous injection (as placebo control) via a 25-G needle. Goal enrollment is 200 patients with 100 patients in each group. Patients included in the study will be followed during inpatient hospitalization through discharge.

6. Research data collection/study procedures:

Intervention

Patients will be identified on admission and will be screened by inclusion/exclusion criteria. After informed consent is obtained they will be randomized into one of two possible groups:

- a. Liposomal bupivacaine intercostal (group 1; interventional)
- b. 0.9% sodium chloride peri-intercostal subcutaneous (group 2; placebo-control)

Patients will be placed on continuous monitoring of heart rate, EKG, and pulse oximetry. Blood pressure and respiratory rate will be measured every 5 to 10 minutes during the procedure and every at least 15 minutes for the first hour after the procedure. All patients undergoing injection will remain on heart rate, EKG, and pulse oximetry monitoring by telemetry for 96 hours following injection.

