In addition, while in the ICU all study subjects will be monitored with a non-invasive respiratory monitor (Expiron) to determine respiratory rate, tidal volume, minute volume and breathing pattern for up to 96 hours. This monitoring will aid in

detection of respiratory depression and add additional safety to the trial. This device measures chest expansion by thoracic impedance and is FDA approved.

Supplemental oxygen will be provided to maintain a peripheral oxygen saturation of 90% or greater.

Injections will be performed by trained trauma / critical care physicians. Training prior to initiating the study will include familiarization with the standardized procedure as described below, which will be documented in study records. Patients will be monitored by bedside nurses before, during, and after the block procedure. Standard inpatient cardiac arrest carts will be immediately available before, during, and after the block procedure.

A 20-mL vial will be obtained from IDS Pharmacy that either contains liposomal bupivacaine (266 mg in 20-mL) or 0.9% sodium chloride. Patients will be positioned either sitting up or in logroll/decubitus position. Rib fractures will be noted from previously obtained CT scan of the chest from initial trauma evaluation. The thoracic posterolateral area will be prepped and draped in sterile fashion. After aspiration to prevent intravascular injection, 1 mL of liposomal bupivacaine will be injected with a 25-G needle just below each affected rib by the intercostal neurovascular bundle in a posterior but not paravertebral position or 0.9% saline (as placebo control) will be injected with a 25-G needle in the subcutaneous space just superficial to each affected rib to minimize risk of placebo-injection complications. Optimal regional blockade will include the rib immediately above the most superior and the rib immediately below the most inferior fractured rib.

Regional blockade will only be performed once per patient enrolled in the study and at one injection site per fractured rib. Patients will only be enrolled once per acute traumatic event and admission.

If a patient enrolled in the study should have an adverse event during the course of intercostal rib block administration and the reaction is severe or life-threatening, then the patient will be withdrawn from the study and no further injections will be administered, regardless of how many injections were originally planned.

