Liposomal bupivacaine offers formulation that provides prolonged yield of the anesthetic properties up to 96 hours. It has been shown to improve analgesia scores and decrease opioid requirements when used locally at surgical sites such as bunionectomies and hemorrhoidectomies (Figure 1a). It has also been shown to reduce the time to first opioid dose needed (Figure 1b). Reductions in opioid requirements have also been appreciated.

Figure 1. Cumulative postsurgical pain score in hemorrhoidectomy patients¹⁵

[figure not shown]
[figure not shown]

Figure 2. Cumulative portion of patients requiring opioid therapy post-hemorrhoidectomy¹⁵

Patients randomized into the standard analgesia plus placebo intercostal injection group will benefit from increased nursing attention to pain score assessment and treatment as well as increased respiratory therapist attention to pulmonary toilet and objective assessments of spirometry volume capacities. Patients randomized into the standard analgesia plus liposomal bupivacaine group will additionally receive the anticipated benefit of intercostal nerve blocks for improved analgesia.

In addition, all subjects will be monitored with a non-invasive respiratory monitor (Exiron) to determine respiratory rate, tidal volume, minute volume and breathing pattern. This monitoring is in addition to standard care and will aid in detection of respiratory depression and add additional safety to the trial.

Future patients can benefit from the cultivation of this knowledge to have both potential patient benefit (e.g., decreased morbidity and mortality; improved pain scores; decreased risk of pneumonia) and cost-savings (e.g., decreased medication requirement; less time in the ICU or hospital). Overall, optimal use of liposomal bupivacaine may help improve patient pain scores, pulmonary toilet and ability to use IS, and decrease the need for opioid therapy. Improved patient outcomes, expansion of scientific knowledge, and development of new blunt chest wall trauma pain protocols may result.

9. Potential Risks, Discomforts, and inconveniences:

Level of Risk

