There may be temporary pain or local discomfort associated with repeated intercostal injections. Additionally, there will be a small risk of a pneumothorax if the intercostal injection needle violates the parietal pleura.

Additionally, the trauma team will have discretion to hold or stop enoxaparin doses if patient is deemed to have bleeding. Patients may also have doses held due to perioperative plans. This will also allow for appropriate, safe patient care.

If a patient enrolled in the study should have an adverse event during the course of the intercostal rib block administration and the reaction is severe or life threatening, then the patient will be withdrawn from the study and no further injections will be administered, regardless of how many injections were originally planned. In addition, an adverse event based on physiologic response will include a sustained (greater than five minute) change in heart rate by > 40% from baseline or absolute heart rate greater than 160 or less than 50, change in systolic blood pressure by 40% or absolute systolic blood pressure less than 80 mmHg or greater than 180 mmHg, change in respiratory rate by 50% or absolute respiratory rate greater than 30 or less than 6, or decreasing oxygen saturation

by 10% SpO₂ or less than absolute SpO₂ < 85%. Any non-sinus rhythm or ST segment changes seen on the EKG monitoring strip will lead to immediate subject discontinuation.

Safety Assessments

Every adverse event, whether or not thought to be related to study drug, will be recorded and entered into the RAVE Case Report Form database.

Any medical condition present prior to study enrollment should not be reported as an adverse event, unless the medical condition worsens in severity or seriousness during the study. In this case it may be reported as an adverse event at the discretion of the Investigator.

The Investigator will review each event and assess its severity and relationship to the study treatment.

Adverse event Definitions:

Adverse Event

Adverse event means any untoward medical occurrence associated with the use of a drug in humans, whether or not considered drug related.

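### The protocol gives two scopes for the respiratory monitor, ICU time only or all subjects; under the ICU-only wording, events found only by the monitor may be under-recorded in the arm with less ICU time in the first 96 hours

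*Combined protocol and SAP*

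**What the plan says.** Section 6, Intervention, limits the device by location: "while in the ICU all study subjects will be monitored with a non-invasive respiratory monitor (Expiron". Its readings are used "to determine respiratory rate, tidal volume, minute volume and breathing pattern for up to 96 hours".

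Section 8, Potential Benefits, describes the same device with neither an ICU condition nor a duration: "all subjects will be monitored with a non-invasive respiratory monitor (Exiron) to determine respiratory rate, tidal volume, minute volume and breathing pattern". It presents this as a gain for participants: "This monitoring is in addition to standard care and will aid in detection of respiratory depression".

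Two other rules in section 6 apply to every patient wherever they are. Around the injection, "Blood pressure and respiratory rate will be measured every 5 to 10 minutes during the procedure", then at least every 15 minutes for the first hour. After that, "All patients undergoing injection will remain on heart rate, EKG, and pulse oximetry monitoring by telemetry for 96 hours following injection". The telemetry list does not include respiratory rate. A later paragraph of section 6, on the schedule of data collection, says that vitals monitoring continues by telemetry for 96 hours or until discharge, and does not name respiratory rate either.

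Section 9 (Level of Risk) includes among its physiologic adverse event criteria a "change in respiratory rate by 50% or absolute respiratory rate greater than 30 or less than 6", next to criteria for heart rate, blood pressure and oxygen saturation. Every adverse event is to be recorded. Section 11 lists ICU length of stay as secondary endpoint 1e.

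**The concern.** There are two problems. The first is the contradiction. A patient who never enters the ICU gets none of the added monitoring under section 6, yet section 8 counts that monitoring as a benefit for everyone.

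The second is ascertainment. If the monitor runs only in the ICU, the intensity of respiratory surveillance depends on something that happens after randomisation and that the treatment may affect. Section 8 names less time in the ICU as a hoped-for gain. With equal true risk, the arm that leaves the ICU earlier would have fewer monitored hours and could record fewer monitor-detected events. A reader of the safety tables could mistake that for a treatment effect on respiratory safety, which matters in a trial that added the device to help detect respiratory depression.

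**Working it through.** **Step 1. Which respiratory observations depend on location, under the section 6 wording?**

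| Observation | Who and when | Depends on ICU? |
|---|---|---|
| Respiratory rate checks | All, during the procedure and the first hour | No |
| Pulse oximetry by telemetry | All injected patients, 96 h | No |
| Daily follow-up by coordinators and trauma physicians | All, first 96 h | No |
| Portable spirometry | All, daily | No |
| Monitor: respiratory rate, tidal volume, minute volume, breathing pattern | ICU only, up to 96 h | Yes |

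After the first hour, the last row is the only specified source of respiratory rate. Under the section 8 wording that row becomes independent of location and the ascertainment problem disappears.

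**Step 2. How large could the effect be?** The plan states no figure to reproduce. It gives no respiratory event risk, no expected ICU hours and no detection rates, so every input below is an assumption except the 96-hour window (section 6) and 100 patients per arm (section 5, Study design). Events are assumed to be spread evenly over the 96 hours, and true risk is equal in the two arms.

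*Illustration A.* True risk 20%; 90% of events detected on the monitor; a fraction d detected elsewhere; h hours in the ICU.

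Recorded risk = 0.20 × [0.9 × h/96 + d × (1 − h/96)]

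| d | h = 48 | h = 24 | Apparent reduction |
|---|---|---|---|
| 0.1 | 0.20 × (0.45 + 0.05) = 10% | 0.20 × (0.225 + 0.075) = 6% | 40% |
| 0.3 | 0.20 × (0.45 + 0.15) = 12% | 0.20 × (0.225 + 0.225) = 9% | 25% |
| 0.5 | 0.20 × (0.45 + 0.25) = 14% | 0.20 × (0.225 + 0.375) = 12% | 14% |

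The absolute gap is 2 to 4 percentage points.

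*Illustration B.* This varies the ICU contrast. Let f = min(ICU hours, 96)/96, and let s be detection outside the ICU relative to inside. The true risk R cancels from the ratio:

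Ratio of recorded events = [f₂ + s(1 − f₂)] / [f₁ + s(1 − f₁)]

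| ICU hours, arm 1 vs arm 2 | s = 0 | s = 0.5 | s = 0.8 | s = 1 |
|---|---|---|---|---|
| 72 vs 60 | 0.83 | 0.93 | 0.97 | 1.00 |
| 72 vs 48 | 0.67 | 0.86 | 0.95 | 1.00 |
| 96 vs 48 | 0.50 | 0.75 | 0.90 | 1.00 |
| 72 vs 72 | 1.00 | 1.00 | 1.00 | 1.00 |
| 120 vs 96 | 1.00 | 1.00 | 1.00 | 1.00 |

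For example, 72 vs 48 with s = 0.5 gives (0.5 + 0.25)/(0.75 + 0.125) = 0.75/0.875 = 0.86.

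*Chance of a spurious finding.* With R = 10%, 100 per arm and 72 vs 48 hours, the normal-approximation chance of a two-sided p < 0.05 favouring the arm with less ICU time is 11% at s = 0, 5% at s = 0.5 and 3% at s = 0.8. Without bias, that one direction would give 2.5%. The most extreme case tried (R = 20%, 96 vs 48 hours, s = 0) gives 51%, but s = 0 means that nothing is found outside the ICU, which Step 1 rules out.

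**Step 3. What must be true for any bias?** The arms must differ in ICU hours within the first 96 hours; stays beyond that add nothing (last row). Some events must be visible only on the monitor. Those readings must also be entered as adverse events, and no section says how that would happen.

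**The case against.** A reader might infer that detection of respiratory adverse events as a whole begins and ends with the ICU stay, and that the arm leaving sooner is therefore bound to look safer. The documents do not support either statement. Oximetry runs for 96 hours in all injected patients, and an oxygen saturation fall is itself an adverse event criterion. All patients are followed daily and every adverse event is recorded. Any bias also needs the conditions in Step 3.

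Four further objections carry weight.

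- The respiratory-rate criterion in section 9 sits in a paragraph that opens with events during block administration. If it is meant only for that period, respiratory rate is measured then in every patient and ICU time is irrelevant. The paragraph sets no time limit, so both readings are open.
- Section 11 names no respiratory adverse event comparison, and section 6 (Data Collection) ties the safety evaluation to serious adverse events set in advance. Intubation or death would be noticed on any ward.
- The stopping rules in section 10 are percentages of all enrolled patients, so a difference in ascertainment between arms does not enter them directly.
- Enrolment is planned within 6 hours of admission. First ICU placement may often precede injection and be balanced by randomisation, leaving mainly the time of leaving the ICU as the route to bias.

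These points narrow the concern without removing it. Oximetry does not replace a respiratory-rate channel: section 6 provides supplemental oxygen to hold saturation at 90% or above, while the section 9 criterion is a 10% fall or a value below 85%. Daily follow-up is not continuous surveillance. Table 9.4 grades respiratory rates from 17 breaths upward, so closer measurement is likely to find more gradable values. The contradiction between sections 6 and 8 is untouched by any of this.

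**Conclusion.** The contradiction is certain and rests on the text alone: sections 6 and 8 give different answers on who is monitored, and no other section resolves it.

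The ascertainment bias is conditional. Under the ICU-only wording, monitor-detected respiratory events may be under-recorded in the arm with less ICU time within the first 96 hours. The bias is limited to events found only by the monitor and recorded as adverse events, and it is zero when ICU time in that window is equal.

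Its size cannot be derived from the documents. The 14% to 40% range holds only for the inputs of Illustration A; with good detection outside the ICU (s = 0.8) the ratio is 0.90 to 0.97 across the unequal ICU contrasts tried. Neither figure is a forecast. The point warrants a correction to the plan, but does not support a claim that the safety comparison is bound to be biased.

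**What to change.** 1. Reconcile sections 6 and 8 so that the protocol states one monitoring scope. If it stays ICU-only, correct the benefit statement in section 8. Which scope to adopt is for the sponsor and the investigator.
2. State in section 9 whether the respiratory-rate criterion applies only around the procedure or throughout the 96 hours, and how monitor readings become adverse events.
3. In section 11, base any between-arm comparison of respiratory events on observations made in all patients, wherever they are, over the same window.
4. Record the source of detection for each respiratory event and the monitored hours for each patient. Report monitor-only events separately by arm, per monitored hour.

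The cost is one case report form field, the monitored hours, and wording in sections 6, 8, 9 and 11. The small downside is that monitor-only events leave the main between-arm comparison; they are still recorded and reviewed for safety. If every patient has the same monitoring window whatever their location (s = 1), the ratio in Illustration B is 1.00 for any ICU hours and the artefact disappears.

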Following informed consent, patients will undergo 2x1 block randomization to ensure equal allocation to each intervention group. Randomization will be performed by study personnel and will be blinded as there will be placebo injections for patients randomized into group two and the same number of injections would be used regardless of intervention arm.

Data Collection:

Verbal NRS, pain assessment data, opioid use, and time to first opioid breakthrough dose will be collected as previously described. Portable spirometry will be used daily to objectively and serially assess lung function. Additional data collection points include patient sex, age, weight, body mass index, body surface area, injury severity score, chest abbreviated injury score, and ICU and hospital length of stay. Safety will be evaluated by the occurrence of *a priori* serious adverse events. Costs will be evaluated utilizing hospital and pharmacy databases.

Schedule of subject identification and data collection

Subjects will be identified based on inclusion criteria at the time of admission to the trauma service following evaluation in the emergency department. Subjects meeting inclusion criteria will be enrolled within 6 hours of admission. Vitals monitoring will occur during the intercostal nerve block procedure and continue by telemetry for the next 96 hours or until hospital discharge, whichever occurs first.

7. Specimen collection:

No serum assays are necessary for this study and will not be collected.

8. Potential Benefits:

Blunt chest wall trauma remains a common injury seen in non-intentional injury-related deaths. It accounts for nearly 10% of trauma-related emergency department visits worldwide and is associated with high morbidity and mortality. This morbidity and mortality are influenced by the pain experienced by these events which can involve rib or sternal fractures as instigating stimuli.

Uncontrolled analgesia following rib fractures can result in intubation, pneumonia, prolonged length of stay, and death. Achieving adequate pain control in native airway patients prevents clinical challenges. Multimodal analgesia regimens are necessary to optimize patient outcomes and prevent untoward effects of opioid analgesia (e.g., hypotension; bradycardia; central nervous system depression; respiratory depression).

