Consequences of poorly controlled pain associated with rib and/or sternal fractures as well as opioid use have been previously outlined above. Risks of liposomal bupivacaine include major and minor adverse events (Tables 1 and 2). Risks will be mitigated by appropriate exclusion of patients with low and high body weights as well as known cardiac history as previously described to minimize pharmacodynamic failure or excess.

Table 9.1. Adverse events occurring in >2% of patients in any treatment group^{15,17,31}

Adverse Event	Bunionectomy ^{17, 20}		Hemorrhoidectomy ^{18, 20}	
	Liposomal Bupivacaine 106 mg (n=97)	Placebo (n=96)	Liposomal Bupivacaine 266 mg (n=95)	Placebo (n=94)
Any treatment-emergent adverse event	58 (59.8)	65 (67.7)	16 (16.8)	17 (18.1)
Gastrointestinal disorders				
Nausea	41 (42.3)	38 (39.6)	8 (8.4)	13 (13.8)
Vomiting	39 (40.2)	36 (37.5)	2 (2.1)	1 (1.1)
Painful defecation	27 (27.8)	17 (17.7)	2 (2.1)	4 (4.3)
Nervous system disorders				
Dizziness	20 (20.6)	30 (31.3)	0 (0.0)	0 (0.0)
Headache	11 (11.3)	25 (26.0)	0 (0.0)	0 (0.0)
Somnolence	5 (5.2)	8 (8.3)	0 (0.0)	0 (0.0)
Skin and subcutaneous tissue disorders				
Skin and subcutaneous tissue disorders	8 (8.2)	7 (7.3)	0 (0.0)	0 (0.0)
Pruritus, generalized	5 (5.2)	6 (6.3)	0 (0.0)	0 (0.0)
Abnormal laboratory investigations	5 (5.2)	3 (3.1)	4 (4.2)	3 (3.2)

Data are no. (%) of patients.

Table 9.2. Incidence of serious adverse events occurring in >1 patient in any treatment group³⁰

	n (%)		
	Liposome Bupivacaine		
	≤266 mg (n = 545)	Bupivacaine HCl (n = 446)	Placebo (n = 190)
Any serious AE	6 (1.1)	24 (5.4)	2 (1.1)
Arthrofibrosis	0	3 (0.7)	0
Cellulitis	0	0	0
Congestive cardiac failure	0	0	0
Atrial fibrillation	0	2 (0.4)	0
Sedation	0	0	0
Hypoglycemia	0	2 (0.4)	0
Deep vein thrombosis	0	2 (0.4)	1 (0.5)

Cardiac and neurotoxicity that are generally seen with increased serum bupivacaine concentrations (i.e. >2000 ng/mL) should serve minimal risk as concentrations seen in previous studies using the maximum FDA-approved dose of 266 mg of liposomal bupivacaine measured maximum concentrations of 867 and <300 ng/mL each.^{15, 28-29} Patients will require and be monitored by a central cardiac monitoring unit to assess for any changes in heart rate or rhythm for the first 96 hours at minimum.

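### The 20-fracture ceiling leaves no volume for the adjacent ribs the procedure adds, and the text supports two doses for the same injury

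*Combined protocol and SAP*

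**What the plan says.** Four places bear on how much study drug a patient is meant to receive.

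- **Section 6, Intervention (supply and volume).** "A 20-mL vial will be obtained from IDS Pharmacy that either contains liposomal bupivacaine (266 mg in 20-mL) or 0.9% sodium chloride". In the active arm, "1 mL of liposomal bupivacaine will be injected with a 25-G needle just below each affected rib". The word *affected* is not defined.
- **Section 6, Intervention (which ribs).** "Optimal regional blockade will include the rib immediately above the most superior and the rib immediately below the most inferior fractured rib". The next paragraph says that the block is done once per patient and "at one injection site per fractured rib".
- **Section 13, exclusion f.** "Patients with greater than 20 rib fractures (20-mL vial [266-mg dose]; 1-mL [13.3 mg] per rib". The ceiling is therefore derived from the vial volume.
- **Section 9, Level of Risk.** The reassurance on systemic toxicity refers to concentrations measured at "the maximum FDA-approved dose of 266 mg of liposomal bupivacaine".

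Two further statements depend on the number of sites. Section 6 (Randomization) supports the blinding by saying that "the same number of injections would be used regardless of intervention arm". Section 11 lists, as a secondary endpoint, the calculation of local anesthetic dose and exposure, including that from the intercostal blocks.

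**The concern.** Exclusion f works only if fractured ribs alone are injected. The first of the two section 6 sentences on sites adds one rib beyond each end of the fractured segment; the second, on its plain reading, does not. An operator cannot tell from the text which applies, and the eligibility ceiling agrees with only one of them.

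Three things are at stake.

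1. **The ceiling.** For the most heavily injured eligible patients the planned sites can need more than the single vial. No rule says which ribs are then left out, or whether the volume per site is reduced.
2. **The dose for a given injury.** Two patients with the same fractures can receive different amounts of active drug, depending on which sentence the operator follows. This adds avoidable variation to the treatment being tested.
3. **The equal-injection claim.** Active drug is placed beside the neurovascular bundle and placebo in the subcutaneous space, so the person injecting can tell the arms apart. If the number of sites is left to that person, nothing in the text fixes it before the arm is known.

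**Working it through.** **Inputs**

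- Vial: 20 mL containing 266 mg (section 6, Intervention; section 13, exclusion f).
- Volume: 1 mL per rib (same places).
- Adjacent ribs: one above and one below (section 6, Intervention).
- Entry range: at least 2 rib or sternal fractures (section 13, inclusion b) and at most 20 rib fractures (exclusion f).
- Assumptions not in the documents: each adjacent rib also receives 1 mL, each fractured rib has one fracture, and an unfractured rib exists at each end.

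**Step 1. Reproduce the plan's figure.** Concentration = 266 / 20 = 13.3 mg per mL. With fractured ribs only, 20 × 1 mL = 20 mL and 20 × 13.3 = 266 mg. The stated ceiling reproduces exactly and leaves 20 − 20 = 0 mL for any other rib.

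**Step 2. Add the two adjacent ribs.** For n fractured ribs, volume = (n + 2) × 1 mL and dose = (n + 2) × 13.3 mg.

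| Fractured ribs | Fractured only | With two adjacent ribs | Above one vial? |
|---|---|---|---|
| 2 | 2 mL, 26.6 mg | 4 mL, 53.2 mg | no |
| 6 | 6 mL, 79.8 mg | 8 mL, 106.4 mg | no |
| 18 | 18 mL, 239.4 mg | 20 mL, 266.0 mg | no, exactly used |
| 19 | 19 mL, 252.7 mg | 21 mL, 279.3 mg | yes |
| 20 | 20 mL, 266.0 mg | 22 mL, 292.6 mg | yes |

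At 20 fractured ribs the planned volume is 22 / 20 = 1.10 times the vial, or 10% over.

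**Step 3. Compare the two doses at the same count.** The gap is always 2 × 13.3 = 26.6 mg, and the ratio is (n + 2) / n. That is 4 / 2 = 2.00 at 2 fractured ribs, 8 / 6 = 1.33 at 6, and 22 / 20 = 1.10 at 20. The relative ambiguity is largest in the least injured patients.

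**Step 4. Check how firm the overrun is.** Exclusion f counts fractures, whereas injection is by rib. Twenty fractures in 18 ribs would need 18 + 2 = 20 mL, which fits. A fracture of the first or last rib leaves no rib to add at that end. The overrun therefore depends on the fracture pattern. The documents give no distribution of fracture counts, so its frequency cannot be estimated.

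**The case against.** The best defense is that the wording can be read consistently. *Optimal* may express an aim, and the limit of one site per fractured rib may only bar repeat injections at the same rib. On that reading adjacent ribs are optional extras, and up to 18 singly fractured ribs plus two fit in the vial. If adjacent ribs are never injected, the ceiling of 20 is also consistent. What stands is that such readings exist. They do not settle the matter, because treating the adjacent ribs as optional leaves the site count to the operator, in a procedure that section 6 describes as standardized.

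Four stronger readings are tempting, and the documents do not support them.

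- **Patients will receive more than 266 mg.** Section 6 supplies one vial and allows one block per patient. The figures above 266 mg are planned amounts that a single vial cannot deliver. Nor does section 9 rest on the dose alone: it sets a toxicity level above 2000 ng/mL against measured maxima of 867 and below 300 ng/mL.
- **Four adjacent ribs in bilateral injury.** This would give 24 mL (319.2 mg) at 20 fractured ribs, but the text names a single rib at each end and does not mention counting by side.
- **Site counts will differ by arm.** Section 6 (Randomization) requires equal counts. The operator's knowledge of the arm makes a difference possible; it does not show that one will occur.
- **A dose that varies between patients is itself an error.** Dose is meant to follow the number of ribs. The fault is that it is not determined for a given number.

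It is also fair to say that the dose endpoint in section 11 implies that injected volume will be captured. However, the data items listed in section 6 do not name the number of sites.

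**Conclusion.** The point holds as a contradiction between a dosing instruction and the eligibility threshold derived from it, which is more than missing detail. With two adjacent ribs at 1 mL each and one fracture per rib, the planned volume passes one vial at 19 fractured ribs (21 mL, 279.3 mg) and is 10% over at 20 (22 mL, 292.6 mg). No rule covers the shortfall. At every count the text supports two doses 26.6 mg apart: twofold at 2 fractured ribs and one-third higher at 6.

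The 1 mL for an adjacent rib is inferred from the per-rib volume in exclusion f. The overrun concerns the top of the eligible range only, and its frequency is unknown. The effect on the comparison of arms is a risk that the plan leaves open, and no size can be put on it. No view is taken on which dose or which set of ribs is right.

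**What to change.** The sponsor should reconcile the two section 6 sentences with exclusion f and, in doing so:

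- define *affected rib*, and state one rule for which ribs are injected;
- state what is done if the planned sites exceed the vial;
- have the number of sites set from the CT before the arm is known, and applied equally in both arms, so that the equal-injection statement in section 6 (Randomization) is supported;
- make the eligibility ceiling and its mL and mg rationale agree with the rule chosen, including whether it counts fractures or ribs;
- record the number of sites injected per patient, for the dose endpoint in section 11.

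The content of the rule is a clinical decision for the sponsor. The cost is a wording amendment and one data item. Depending on the rule chosen, eligibility may change for a few patients with very many fractures.
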